#### **Week 24**

All women treated by thermocoagulation and had CIN1+ detected by baseline cervical biopsy will return at Week 24 for colposcopy to assess for resolution of cervical dysplasia after thermocoagulation. HPV testing on a provider-collected vaginal brush will also be performed at Week 24 to assess for HPV resolution after thermocoagulation. If the colposcopy shows no visible lesions at this Week 24 visit,

cervical pap smear and ECC will be collected. If a lesion is observed during colposcopy, at least 2 but not more than 4 directed biopsies and ECC will be performed. Images may be captured via the EVA System. These images will be stored only in password-protected and de-identified study databases, linked only to the study participant PID. The images will be used for internal quality assurance and possibly shared in de-identified form for future research. All women who still have CIN2/3 or have developed CIS or ICC at Week 24 will be referred to KCH for additional management. Women will also be evaluated for changes in their interval medical history and post-treatment adverse events during this visit. Finally, all women who were referred to KCH Colposcopy Clinic will be followed up at this visit to ensure that they received the care they required.

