## 5.0 TIME AND EVENTS TABLE

### 5.1 Schedule of study procedures

Study Visit	Screening & Enrollment	Week 4	Week 24	Week 28
Women who will attend the study visit	All women	Women who had cervical biopsy or cervical pap smear, and ECC done at Screening & Enrollment	Women who had CIN1+ at Screening & Enrollment and underwent thermocoagulation	Women who attended the Week 24 Visit
Evaluations				
Informed consent	X			
Baseline survey	X			
Urine pregnancy testing	X	X	X	
HIV-1 Rapid Test (2 kits)	X			
HIV-1 Confirmatory Test 	X			
CD4+ T cell count 	X			
HIV-1 RNA (plasma) 	X			
Self-collected vaginal brush	X			
hr-HPV testing of self-collected samples	X		X	
hr-HPV and S5 methylation testing of urine sample	X			
Provider-collected cervical brush	X 		X	
hr-HPV testing of provider-collected cervical sample	X 			
S5 methylation testing of provider-collected cervical sample	X 			
VIA 	X			
Colposcopy and cervical biopsy or cervical pap smear, and ECC 	X		X	
Thermocoagulation 	X			
Thermocoagulation-related adverse events evaluation		X		
Provide results and any referrals		X		X
Follow-up questionnaire 		X		
Enroll for IDIs	X	X		

For those with discordant HIV rapid tests.

For HIV-positive participants only

For all hr-HPV+ and for every 10th woman who is hr-HPV-.

Cervical biopsy and ECC if lesion seen at colposcopy; Cervical pap smear and ECC if no lesion seen at colposcopy

For women with ablation-eligible cervical lesion at colposcopy.

For follow-up of cervical histology and/or cytology results from Screening/Enrollment and to assess for any change in history or adverse events from thermocoagulation (if thermocoagulation was performed).

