### 6.2 Sample Size and Accrual

We anticipate enrolling 625 women over approximately 260 days. This enrollment target assumes a screening to enrollment ratio of 10 to 9, with 2-3 women enrolled/day, which is very feasible and allows adequate time for informed consenting, same-day screening with hr-HPV testing, triage with VIA, and thermocoagulation for VIA positive, ablation-eligible (by colposcopy) women, and also sufficient time for scheduled follow-up visits for already-enrolled women. Based on prior studies done among HIV-positive women in SSA, we assume that at least 50% (n=313) of the 625 HIV-positive women will be positive for hr-HPV and that at least 20% of these 313 women will have CIN2/3, which gives us at least 63 HIV-positive women with CIN2/3 in our cohort. Among HIV-negative women, we assume that at least 20% (n=125) of the 625 HIV-negative women will be positive for hr-HPV and that at least 10% of these women will have CIN2/3, which gives us at least 13 HIV-negative women with CIN2/3 in our cohort.

We assume that 5% of the 76 women with CIN 2/3 will be lost-to-follow-up after 24 weeks (95% is the typical rate of retention for studies done at UNC Project-Malawi at 6-month follow-up). Therefore, we will be able to determine the 24-week efficacy of thermocoagulation among approximately 72 women, including 60 HIV-positive women, with CIN2/3. This sample size of 72 CIN2/3 women, 60 of whom are HIV-positive, is comparable with other studies included in a meta-analysis that evaluated the efficacy of thermocoagulation for treating CIN2/3. Assuming treatment efficacy of 90% over 24-weeks follow-up, we should have >95% confidence to measure the efficacy within  $\pm$  8% for the overall sample and the HIV-positive sub-group.

For the IDIs, up to 30 women will be recruited at Screening/Enrolment Visit or Week 4 Visit. The IDIs will explore participants' experiences with the proposed ICC screen-and-treat strategy among women. We expect to reach thematic saturation with this sample size, based on prior work showing that few new themes are established after the first 18 interviews. We expect significant overlap in themes between the HPV-positive and HPV-negative groups.

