**Primary objective II:** To determine the 24-week efficacy of thermocoagulation among women, including HIV-positive women, with CIN2/3. Women who undergo thermocoagulation will have follow-up at 24-weeks post-treatment for colposcopy, provider collected cervicovaginal brush for hr-HPV testing, ECC, colposcopy-directed cervical biopsy and ECC (if lesion noted) or cervical cytology and ECC (if no lesion noted at colposcopy). We hypothesize that >90% with CIN2/3 on pre-treatment biopsy will have  $\leq$ CIN1 at their 24-week biopsy.

**Data analysis for primary objective II:** For efficacy of thermocoagulation, we will compare our 24-week cure rates for CIN 2/3 with thermocoagulation to historic cure rates for CIN 2/3 with cryotherapy (85-95%), the recommended ablative treatment modality for CIN 2/3 for resource limited countries. We will perform exploratory analysis to determine the following:

- a) 24-week efficacy for CIN1, by calculating the proportion of women who had CIN1 at Screening/Enrollment and then were found to have no cervical dysplasia at Weeks 24 after thermocoagulation treatment;
- b) hr-HPV clearance in HPV-positive women treated with thermocoagulation, by calculating the proportion with no hr-HPV at Weeks 24; and
- c) Risk factors for CIN2+ among HPV-positive women (i.e., age, age at first sexual intercourse, number of sexual partners, HIV status, length of time on ART, HIV-1 RNA load, CD4+ count) via multivariable logistic regression.

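### The primary 24-week cure criterion rests on a biopsy that only women with a visible lesion receive, and no rule maps Week 24 ECC, cytology or later treatment to cure or failure

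*Combined protocol and SAP*

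**What the plan says.** **Criterion.** Section 6.3, Primary objective II, hypothesises that more than 90% of women with CIN2/3 on pre-treatment biopsy will be no worse than "CIN1 at their 24-week biopsy". The analysis paragraph then compares the 24-week cure rate with a historic 85-95% for cryotherapy, without defining cure further.

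**Week 24 specimens.** The sentence before the hypothesis provides for biopsy and ECC if a lesion is noted, or "cervical cytology and ECC (if no lesion noted at colposcopy"). Section 4.3 (Week 24) makes the same split, beginning "If the colposcopy shows no visible lesions at this Week 24 visit". Footnote 4 of the section 5.1 schedule agrees: "Cervical pap smear and ECC if no lesion seen at colposcopy".

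**Denominator.** Section 6.2 says the study will be able to "determine the 24-week efficacy of thermocoagulation among approximately 72 women, including 60 HIV-positive women, with CIN2/3", with precision of ±8% at 90% efficacy. The completion indicators in section 6.3 count resolved and persistent CIN2+ among treated women who return at Week 24, but define neither term. The exploratory CIN1 analysis counts women "found to have no cervical dysplasia at Weeks 24 after thermocoagulation treatment", also without reference to a biopsy.

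**Further treatment.** Section 6.3, Secondary objective I, recognises that some thermocoagulated women will have CIN2+ on ECC and need referral. Section 4.3 (Week 24) states that "all women who were referred to KCH Colposcopy Clinic will be followed up at this visit", and a completion indicator counts referred women who were managed by Week 24.

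**The concern.** The criterion and the denominator cannot both be applied as written. A woman with no visible lesion at Week 24, who on its face is a likely treatment success, has no 24-week biopsy and so no primary outcome under the stated wording. If failures are concentrated among women with lesions, the women left are enriched for failures and the cure rate is too low.

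Correcting the denominator does not finish the job. The plan does not say whether ECC can stand in for the biopsy, or which cytology result is a cure and which a failure. Nor does it say how to classify a woman with CIN2/3 on baseline biopsy who was thermocoagulated, also had CIN2+ on ECC, and had further cervical treatment before the Week 24 assessment. If she is then clear, nothing prevents her from being credited to thermocoagulation.

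The result is read against a 90% hypothesis and an 85-95% historic range in a single-arm study. Without written rules, these choices would be made with the data in view.

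**Working it through.** **1. The plan's own figures (section 6.2).**
- HIV-positive: 625 × 0.50 = 312.5, taken as 313; 313 × 0.20 = 62.6, taken as 63.
- HIV-negative: 625 × 0.20 = 125; 125 × 0.10 = 12.5, taken as 13.
- Total 63 + 13 = 76. After 5% loss, 76 × 0.95 = 72.2, about 72; HIV-positive 63 × 0.95 = 59.85, about 60.
- Wald half-width at 90%, 1.96 × √(0.9 × 0.1 / n): 6.9 points for n = 72 and 7.6 points for n = 60.

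Both stated figures reproduce. No deduction is made for women without a biopsy.

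**2. How many women must be classifiable for ±8 points?** n ≥ 1.96² × 0.09 / 0.08² = 54.02, so 55. At a 90% rate, up to 72 − 55 = 17 women overall, or 60 − 55 = 5 HIV-positive women, could be unclassified.

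**3. Literal criterion against all returning women.** The documents do not give the share of women without a lesion at Week 24, so the counts k below are assumptions. Take 90% of 72 = 64.8, rounded to 65 cures and 7 failures. Assume that all failures have a lesion and all k no-lesion women are cured. The biopsy-only rate is then (65 − k)/(72 − k).

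| No-lesion women (k) | Biopsied women | Biopsy-only cure rate |
|---|---|---|
| 0 | 72 | 65/72 = 90.3% |
| 18 | 54 | 47/54 = 87.0% |
| 36 | 36 | 29/36 = 80.6% |

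Over all 72 women the rate is 90.3% in every row.

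**4. Cytology rule.** The number of abnormal smears is not given either. Each woman moved from cure to failure costs 1/72 = 1.4 points. If 2 or 4 of the 65 apparent cures had abnormal cytology counted as failure, the rate is 63/72 = 87.5% or 61/72 = 84.7%.

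**5. Further treatment before Week 24.** The number is unknown. If 4 of the 65 apparent cures had it:
- counted as cures, 65/72 = 90.3%;
- excluded, 61/68 = 89.7%;
- counted as failures, 61/72 = 84.7%.

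**The case against.** The strongest reply is that the biopsy wording is loose drafting in a hypothesis sentence. The sentence before it sets out both specimen routes, the analysis paragraph speaks only of cure rates, section 6.2 counts 72 women, and the completion indicators count returning treated women. Testing a 90% cure hypothesis only in women who still show a lesion would be implausible. This stands as to intent: a reader might infer that the sponsor means to analyse biopsied women only, and the documents do not support that. But intent settles only the denominator; it supplies no rule for ECC, cytology or later treatment.

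Other stronger readings also fail:
- *Women without a lesion have no histology.* ECC is taken from every woman at Week 24. The gap is that the plan does not say how it counts.
- *The ±8% holds only if every woman is classified.* Fifty-five suffice at 90%.
- *The literal rule must bias the rate downward.* That depends on failures concentrating among women with visible lesions.
- *Section 4.3 (Week 4) omits referral of women with CIN2+ on ECC.* It covers HPV-positive/VIA-negative women; only treated VIA-positive women go unmentioned there.
- *Many cures will be due to later treatment.* The primary group requires CIN2/3 on pre-treatment biopsy, so women with CIN2+ on ECC alone fall outside it. The ablation criteria in section 4.3 (Screening & Enrollment) require ectocervical lesions, and suspected endocervical dysplasia is referred, so the number should be small. Nor do the documents establish that referral leads to treatment before Week 24.

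Finally, the study is single-arm, states no formal test or decision threshold, and already collects the specimens needed. That lowers the severity but does not remove the defect.

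**Conclusion.** The criterion is wrong as written and should be fixed; the design itself is not in question. The stated rule, followed exactly, drops women without a lesion from a primary outcome that section 6.2 sizes on all retained women. Outcome rules for ECC, cytology and later treatment are absent.

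The size is illustrative, because the documents give no lesion, cytology or further-treatment counts. Under the assumptions in the working, restricting to biopsied women takes 90.3% to 87.0% or 80.6%, and the handling of four women treated again takes it as low as 84.7%. These shifts cross the 90% hypothesis, and the largest fall below the historic range. The planned precision is more robust: it tolerates 17 unclassified women overall, but only 5 among the HIV-positive.

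**What to change.** In section 6.3, replace the biopsy wording with an outcome over all thermocoagulated women with CIN2/3 on pre-treatment biopsy who are seen at Week 24:

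- **Failure:** CIN2+ on Week 24 biopsy or ECC, or high-grade cytology when no biopsy is taken, with the cytology category fixed in writing before the analysis.
- **Cure:** evaluable results with none of these.
- **No evaluable result:** reported as such and not counted as cured.
- **Further cervical treatment before the Week 24 assessment:** in the main analysis these women stay in the denominator and are not counted as thermocoagulation cures; a sensitivity analysis excludes them.
- **Second sensitivity analysis:** histology only (biopsy or ECC).

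Record further treatment through an explicit prompt in the history already taken at that visit: "Women will also be evaluated for changes in their interval medical history and post-treatment adverse events during this visit". Section 4.3 (Week 4) and section 6.3 (Secondary objective I) must also be reconciled on treated VIA-positive women with CIN2+ on ECC; which clinical rule applies is for the sponsor.

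**Cost.** An amendment is needed, which under section 7.5 goes to both the UNC IRB and the Malawi NHSRC for approval. No new specimen or visit is required. The cure rate may be lower than under a looser rule by an amount that cannot be stated now, and cytology is a less specific failure criterion than histology, hence the histology-only analysis.

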### **2.2 Secondary Objectives**

- 2.2.1. To evaluate performance of the proposed ICC screen-and-treat strategy among women, including HIV-positive women, by estimating overtreatment for women who are HPV-positive/VIA-positive/ablation-eligible, and undertreatment among HPV-positive/VIA-negative women.

2.2.2. To explore women's experiences with the proposed ICC screen-and-treat strategy.

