## 6.0 STATISTICAL CONSIDERATIONS

### 6.1 Study Design

This is a single arm, prospective study of 1,250 women (625 HIV-positive and 625 HIV-negative) recruited from outpatient clinics in Lilongwe, Malawi. The primary objectives of this study are to assess completion of a novel ICC screen-and-treat strategy among women, including HIV-positive women, in Lilongwe, Malawi, using self-collected vaginal brush for hr-HPV testing, followed by same-day VIA and thermocoagulation for HPV-positive/VIA-positive/ablation-eligible (by colposcopy) women, and to determine the 24-week efficacy of thermocoagulation among women with CIN2/3. The secondary objectives will be to evaluate the performance of the ICC screen-and-treat strategy by estimating overtreatment for women who are HPV-positive/VIA-positive/ablation-eligible, and undertreatment among HPV-positive/VIA-negative women, and to explore women's experiences with the proposed screen-and-treat algorithm.

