women who are HPV positive/VIA positive/ablation-eligible, and undertreatment among HPV positive/VIA negative women. All HPV positive women and every 10th consecutive HPV-negative woman will undergo VIA. During VIA, we will determine if a woman is VIA-positive and ablation-eligible. Women who are VIA-positive will undergo colposcopically-directed cervical biopsies and endocervical currettings (ECC). If the woman is still considered to be ablation-eligible by colposcopy, she will then undergo thermocoagulation. Women who are VIA-negative will also undergo colposcopy, but they will only have cervical biopsies and ECC performed if a lesion is seen on colposcopy. Following VIA, we will collect directed cervical biopsies and ECC from VIA positive women prior to thermocoagulation treatment if ablation-eligible by colposcopy, or cervical pap smear and ECC from VIA negative women if no lesion is seen at colposcopy. If a lesion is seen at colposcopy, VIA negative will also undergo colposcopically-directed cervical biopsy and ECC. We hypothesize that <25% of HPV positive/VIA positive women would have been overtreated (no CIN2+, but treated) and that <30% of HPV positive/VIA negative women would have been undertreated (CIN2+, but untreated).

Data analysis for secondary objective I: Overtreatment will be calculated as the proportion of HPV positive/VIA positive/ablation-eligible women who would have been treated with thermocoagulation based on their HPV and VIA findings alone (without colposcopy), but were found to have no CIN2+ on colposcopically-directed cervical biopsy or ECC at Screening/Enrollment. This proportion will represent the women with no lesions or low-grade lesions (CIN1) who would have been unnecessarily treated if we based the decision to perform thermocoagulation on HPV and VIA testing alone.

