Undertreatment will be calculated as the proportion of women with CIN2+ at Screening/Enrollment who were not treated or referred via our screening algorithm due to a negative HPV and/or VIA result. This proportion will represent the women with CIN-2+ who were missed by our HPV-and-VIA-based algorithm. For undertreatment, we will also evaluate the proportion of women who underwent thermocoagulation but were ECC positive for endocervical CIN2+, and therefore needed to be referred for further management since thermocoagulation does not adequately treat endocervical dysplasia. We have based our hypotheses on a recent review, which found that the pooled estimates for VIA sensitivity and specificity were 0.69 (95% CI 0.54-0.81) and 0.87 (95% CI 0.79-0.92), respectively, as well as from the high false positive rate for VIA found in our pilot study with nurses and clinicians in Malawi. These performance measures, however, were for primary screening, rather than as referral to treatment among HPV positive women.

In addition, to assess the potential for undertreatment of HPV-positive women, we will conduct VIA at Screening/Enrollment for every 10th women who is hr-HPV

negative. This sub-set analysis of HPV negative women undergoing VIA will allow us to control for potential verification bias. As all women will not be referred for verification by colposcopy, using only the histology results on HPV positive women to estimate disease burden could lead to biased inference. To correct for this verification bias, we will utilize the colposcopy results among the random sub-set of HPV-negative women to employ the maximum likelihood method proposed by Zhou. Estimates using this method are valid provided that the histology data are missing at random. This assumption means that for women with the same test results, those who were referred to colposcopy were similar to those that were not. Corrected CIN2+ burden will be estimated using maximum likelihood estimators (MLEs). This secondary objective is largely descriptive and, thus, formal power calculations are not made.

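### The under-30% undertreatment hypothesis and the written calculation use different denominators, and the under-25% overtreatment hypothesis is not supported by the VIA accuracy cited for it

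*Combined protocol and SAP*

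**What the plan says.** Section 2.2 words the second half of secondary objective I as "undertreatment among HPV-positive/VIA-negative women", and section 6.1 repeats it. Section 6.3 sets its hypothesis on that group: "<30% of HPV positive/VIA negative women would have been undertreated (CIN2+, but untreated". Under the data analysis for the same objective, section 6.3 then gives the calculation: "Undertreatment will be calculated as the proportion of women with CIN2+ at Screening/Enrollment who were not treated or referred via our screening algorithm". The misses that it counts are those that arise "due to a negative HPV and/or VIA result". To support it, every tenth HPV-negative woman is examined and a maximum-likelihood correction for verification bias is planned.

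For overtreatment the hypothesis reads "We hypothesize that <25% of HPV positive/VIA positive women would have been overtreated (no CIN2+, but treated", and the calculation reads "Overtreatment will be calculated as the proportion of HPV positive/VIA positive/ablation-eligible women".

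Section 6.3 bases both hypotheses on a review in which "pooled estimates for VIA sensitivity and specificity were 0.69 (95% CI 0.54-0.81) and 0.87 (95% CI 0.79-0.92", and on a pilot study whose VIA false positive rate is called high but not given. It adds that the accuracy figures come from primary screening, not from triage of HPV-positive women, and it calls the objective largely descriptive.

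**The concern.** The hypothesis asks what share of HPV-positive/VIA-negative women have CIN2+, which is one minus the negative predictive value (1 − NPV). The calculation asks what share of women with CIN2+ the algorithm misses, which is one minus its sensitivity. This is more than loose wording, because a woman missed through a negative HPV test cannot belong to an HPV-positive/VIA-negative denominator. A limit set for one quantity has no bearing on the other.

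The overtreatment limit raises a different question: whether the accuracy figures named as its basis lead to it.

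No decision rule depends on either limit, but the report will be read against them. A comfortable pass on undertreatment could reflect the choice of denominator alone, and an overtreatment result that the cited inputs would lead one to expect could look like failure.

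**Working it through.** **Inputs.** Section 6.2: 625 HIV-positive women, at least 50% HPV-positive, at least 20% of those with CIN2/3; 625 HIV-negative women, at least 20% HPV-positive, at least 10% of those with CIN2/3. Section 6.3: VIA sensitivity 0.69 (0.54 to 0.81) and specificity 0.87 (0.79 to 0.92).

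**Plan's own counts.** 625 × 0.50 = 312.5, stated as 313; 313 × 0.20 = 62.6, stated as 63; 625 × 0.20 = 125; 125 × 0.10 = 12.5, stated as 13. The total of 63 + 13 = 76 reproduces. It sits among 313 + 125 = 438 HPV-positive women, a prevalence of 76/438 = 17.4%. The plan shows no derivation of either limit, so there is nothing further to reproduce.

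**VIA by CIN2+ among the 438**, taking CIN2/3 as CIN2+:

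- True positives 0.69 × 76 = 52.4; false negatives 76 − 52.4 = 23.6
- False positives 0.13 × 362 = 47.1; true negatives 362 − 47.1 = 314.9
- VIA-positive 99.5; VIA-negative 338.5

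**Undertreatment, hypothesis denominator (1 − NPV).** 23.6/338.5 = 7.0%. At the favourable interval limits (0.81, 0.92) it is 14.4/347.5 = 4.2%; at the unfavourable limits (0.54, 0.79) it is 35.0/320.9 = 10.9%. If VIA detected no CIN2+ at all: 76/(76 + 314.9) = 19.4%. Reaching 30% at the point estimates needs a CIN2+ prevalence p with 0.31p/(0.31p + 0.87(1 − p)) = 0.30, so p = 0.261/(0.261 + 0.217) = 55%, against 17% planned.

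**Undertreatment, calculation denominator (1 − sensitivity).** Among HPV-positive women with CIN2+: 23.6/76 = 31%, or 19% to 46% over the sensitivity interval. Two things move this figure:

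- *HPV-negative CIN2+ raises it.* Section 6.3, under primary objective II, uses 90% hr-HPV positivity among CIN2/3. Applied here, 1 − 0.90 × 0.69 = 38%. This is an illustration, because section 6.2 counts all 76 cases among HPV-positive women.
- *Incomplete ascertainment lowers it.* VIA-negative women with no lesion at colposcopy have a Pap smear and ECC but no cervical biopsy. If a share *a* of VIA-negative CIN2+ is found, the observed value is 23.6a/(23.6a + 52.4): 29% at a = 0.90 and 25% at a = 0.75. Both values of *a* are assumptions.

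**Overtreatment among HPV-positive/VIA-positive women.** 47.1/99.5 = 47%. At (0.81, 0.92): 29.0/90.5 = 32%. At (0.54, 0.79): 76.0/117.1 = 65%. The prevalence at which overtreatment equals 25% is 3(1 − specificity)/[3(1 − specificity) + sensitivity]: 0.39/1.08 = 36% at the point estimates and 0.24/1.05 = 23% at the most favourable limits.

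**The case against.** **Only one calculation is written.** A reader might infer that the analyst may choose between two definitions. The documents do not support that: section 6.3 states a single calculation and already plans the verification correction. The mismatch lies in the objective and the hypothesis, and most of the repair is wording. This stands.

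**Opposite sides of the limit.** With 7% against 31%, a reader might infer that the two definitions fall on either side of 30%. That does not hold firmly. The cited interval alone gives 19% to 46%, incomplete ascertainment could bring the observed value to 25% to 29%, and HPV-negative cases push it up. What stands is that the values differ greatly.

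**Overtreatment below 25% is ruled out.** A reader might infer this from 47%. The documents do not go that far. The accuracy comes from primary screening, the prevalences are minimum values, and the share of women who are ablation-eligible is not given. None of these supplies a basis for under 25%, however, and a pilot false positive rate described as high would not lower the expected value.

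**Eligibility.** Section 4.3 has eligibility determined using colposcopy, while section 6.3 places it during VIA and frames overtreatment without colposcopy. A reader might infer an outright conflict. Both sections also describe a woman as still being eligible at colposcopy, which suggests a judgement in two stages. This is mainly a matter of wording, but the stage that defines the overtreatment denominator is not stated.

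**Conclusion.** The point holds as an inconsistency of denominators. On the denominator of the hypothesis the plan's inputs give about 7% (4% to 11%), and the 30% limit could not realistically be missed. On the denominator of the written calculation they give about 31% among HPV-positive women with CIN2+ (19% to 46%), higher with HPV-negative cases and lower with incomplete ascertainment. The limit is informative only on the second definition, where the outcome is open.

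The overtreatment limit of 25% is unsupported, not excluded. The cited accuracy gives about 47% at the planned prevalence, and 32% even at the most favourable limits.

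These figures take CIN2/3 as CIN2+, use the minimum prevalences at face value, carry primary-screening accuracy over to HPV-positive women and ignore the ablation-eligible restriction. The fault affects how a descriptive secondary objective is interpreted, and it should be fixed.

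**What to change.** 1. In 2.2, 6.1 and 6.3, word the undertreatment objective and hypothesis to match the written calculation: missed CIN2+ over all CIN2+, corrected for verification. Report CIN2+ among HPV-positive/VIA-negative women separately, labelled as 1 − NPV.
2. Restate both expectations from the stated inputs, with their range, the primary-screening caveat and the ascertainment assumption. Alternatively, drop both limits and report each proportion with a 95% confidence interval.
3. Use HPV-positive/VIA-positive/ablation-eligible women in the overtreatment hypothesis, as the objective and calculation already do. Reconcile sections 4.3 and 6.3 on the stage at which eligibility is judged for this analysis.

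The first two changes cost only wording and less favourable stated expectations. The third is also wording unless the stage chosen is not recorded separately. The case report forms are not in the documents; if a separate judgement is not made, it would need an added assessment and field, and could not be recovered for women already examined. No extra participants or visits are needed.
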